10.4.4 Safety Analyses

Adverse events will be coded as per the CTCAE v5.0. Each AE will be coded once for each patient based on the maximum severity during the assessment period. The relationship of AEs to study intervention will be recorded in addition to the onset date, end date, severity, expectedness, and outcome.

10.4.5 Planned Interim Analyses

The primary endpoint will be defined for the entire cohort and no planned interim analyses will be performed.

10.4.6 Sub-Group Analyses

The primary endpoint is based on toxicity at a dose level. Only 3-6 patients will be included per dose level except for the expansion cohort. Thus, it is not feasible to include sub-group analyses.

10.4.7 Tabulation of Individual Participant Data

Individual participant data will not be tabulated.

10.4.8 Exploratory Analyses

- QOL scores will be summarized at baseline and for each visit. This summarization will include the mean, standard deviation, standard error of measurement, effect size, median, minimum, and maximum. Changes from baseline of health-related quality of life questionnaire mean scores will be evaluated. Total and domain mean scores of patients will be compared by the response. Analyses to explore clinically meaningful change of QOL scores may be performed.
- PFS and OS will be informally compared with historical outcomes.

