1.2.9 Updated Clinical and Efficacy Results (IB version 10, dated 9/21/2020)

Results from ongoing and completed clinical studies have shown that selinexor induces durable antitumor responses across a broad range of relapsed or refractory (RR) hematologic and solid tumor cancers, which is consistent with its proposed mechanism of action. In general, these effects appear to be independent of tumor type or prior treatment(s).

As of 31 March 2020, 3419 patients with hematologic or solid-tumor malignancies had received at least 1 dose of selinexor; in addition, 301 patients received at least 1 dose of selinexor or blinded study treatment (i.e., selinexor or placebo) for a total of 3720 patients. These 3720 patients include 2310 patients from Company-sponsored trials (CSTs; 2009 who received selinexor and 301 who received blinded study treatment), 1201 active patients from Investigator-Sponsored Trials (ISTs) who received selinexor, and 161 patients from the selinexor Expanded Access Program (EAP) who received selinexor; and 9 and 39 patients who received selinexor through clinical trials sponsored by Ono Pharmaceutical Co., Ltd and Antengene, respectively.

The most commonly reported treatment-emergent adverse events (TEAEs) for selinexor in CSTs were nausea (66.1%), fatigue (56.7%), anorexia (includes MedDRA “decreased appetite”; 51.1%), thrombocytopenia (51.0%), anemia (43.5%), vomiting (38.7%), and diarrhea (36.6%), that were generally low-grade and reversible. The TEAEs of thrombocytopenia and anemia, which can be higher grade, were reported primarily in patients with hematologic malignancies.

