3.4 QUESTIONNAIRES (FOR ENGLISH SPEAKING PATIENTS ONLY)

MD Anderson Symptom Inventory for Brain Tumors (MDASI-BT) ([Appendix D](#)) will be performed at baseline, at completion of radiation and at all subsequent follow-up visits.

PROMIS Depression, PROMIS Anxiety, and NeuroQoL assessments ([Appendix E](#) and [Appendix F](#)) will be performed at baseline, at completion of radiation and at all subsequent follow-up visits.

PRO-CTCAE ([Appendix G](#)): Patients will complete a baseline PRO-CTCAE before starting treatment, at completion of radiation and at all subsequent follow-up visits if the patient is able. It takes 5-10 minutes to complete each questionnaire. It will only be completed by the patient, unless changes in vision or weakness make this difficult. If this occurs, then the caregiver may read the questions to the patient or assist with marking the answers as described by the patient. A patient caregiver may complete the questionnaires as a patient-preference proxy if the patient's deficits preclude self-report.

All questionnaires are allowed to be completed within +/- 7 days from the scheduled dates.

Every attempt will be made to collect this data from every patient at each time point. If the patient is a non-English speaker the data will not be collected.

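### PRO-CTCAE is collected but not named in the statistical section, and the QOL summary it appears to fall under does not report how many patients newly reported a severe symptom

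*Combined protocol and SAP*

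**What the plan says.** Section 3.4 sets the schedule: "Patients will complete a baseline PRO-CTCAE before starting treatment, at completion of radiation and at all subsequent follow-up visits if the patient is able". Section 2.4 lists the form in its baseline quality-of-life bullet, and footnote 7 of the study calendar (3.5), which is attached to the PRO-CTCAE row, describes a QOL assessment.

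Section 10 does not mention PRO-CTCAE. The safety analysis (10.4.4) rests on clinician grading: "Adverse events will be coded as per the CTCAE v5.0", and "Each AE will be coded once for each patient based on the maximum severity during the assessment period". For QOL scores, 10.4.8 states: "This summarization will include the mean, standard deviation, standard error of measurement, effect size, median, minimum, and maximum". It adds change from baseline in mean scores, and then: "Total and domain mean scores of patients will be compared by the response". It also allows an exploration of clinically meaningful change, but as an option, with no threshold, instrument or denominator. It does not say whether results are split by dose level. Section 10.4.7 adds: "Individual participant data will not be tabulated".

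**The concern.** Tolerability is part of the primary objective (1.1.1), and PRO-CTCAE is the patient's own account of it. Of the 12 symptoms with fixed items in Appendix G, eight are on the protocol's list of selinexor effects seen in at least 10% of patients (14.1.2.1): nausea, vomiting, reduced appetite, fatigue, dizziness, blurred vision, shortness of breath and difficulty sleeping. Section 1.2.9 puts the most common events at "nausea (66.1%), fatigue (56.7%), anorexia" (the last at 51.1%).

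With 3 to 6 patients per level and up to 9 at the MTD, the result a reader can interpret is how many patients reported a severe symptom that they did not have at baseline. The statistics firmly planned in 10.4.8 do not include that count, and without patient-level tabulation it cannot be taken from a listing. Total and domain means do not suit the form either. As printed, Appendix G has separate ordinal items on frequency, severity and interference, a yes/no item on rash and a not-applicable option for radiation burns, and it defines no total or domain score. A comparison by tumour response is not a toxicity comparison.

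**Working it through.** The plan states no figure on this point, so there is none to reproduce. The question is whether the planned statistics determine the count.

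**Inputs.** Level sizes are 3 to 6, with 9 at the MTD and at most 21 evaluable patients (3.1.5, 10.2). The statistics are those listed in 10.4.8. Appendix G prints words only, so coding None to Very severe as 0 to 4 is an assumption. Severe means a score of 3 or more.

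**Item count in Appendix G.** Two items each for appetite, nausea, vomiting, shortness of breath, dizziness, blurry vision, insomnia and fatigue (8 × 2 = 16), and one each for dry mouth, rash, hair loss and skin burns (4), give 20 fixed items.

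**Mean alone, n = 9.** One patient moving from None to Very severe shifts the item mean by 4/9 = 0.44. A mean of 1.33 (total 12) fits anything from 0 to 4 severe patients. A mean of 2.0 (total 18) fits 0 to 6.

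**Five statistics together, n = 9.**

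| Scores | Sum | Sum of squares | Median | Min, max | Severe |
|---|---|---|---|---|---|
| 0,0,0,2,2,2,2,4,4 | 16 | 48 | 2 | 0, 4 | 2 |
| 0,0,0,1,2,3,3,3,4 | 16 | 48 | 2 | 0, 4 | 4 |

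Both have mean 16/9 = 1.78 and SD √[(48 − 16²/9)/8] = 1.56.

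**How often this happens.** Enumerating every possible set of scores, the share of distinct mean/SD/median/minimum/maximum combinations that fit more than one severe count is:

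- n = 6: 0 of 210
- n = 9: 61 of 652
- n = 21 (all levels pooled): 2761 of 5272

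At n = 3 the minimum, median and maximum are the whole data set. So at 3 or 6 patients the count at a single visit can be recovered, provided the summary is given per item and per level.

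**Newly severe.** This depends on pairing each patient with his or her own baseline, which summaries by visit do not keep. Take n = 9 with baseline 3,3,0,0,0,0,0,0,0. A later visit with the same two patients severe, and one where those two have recovered and two others are severe, both have mean 6/9 = 0.67, mean change 0 and two severe scores. The first has 0 newly severe patients and the second has 2. The same happens at n = 3: from baseline 3,0,0, later scores of 3,0,0 or 0,3,0 both give mean 1.0 and mean change 0, with 0 or 1 newly severe.

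**The case against.** **Severe symptoms are counted elsewhere.** A reader might infer that the number of patients with new severe symptoms is never reported. The documents do not support that. Section 10.4.4 codes each event once per patient at maximum severity and records its onset date, and 8.1.2 defines treatment-emergent events as new or worsened ones. Clinician-graded severe nausea or fatigue is therefore countable. This stands, and it confines the gap to the patient-reported count.

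**A total score is not clearly planned.** A reader might also infer that the protocol averages all 20 items. Section 10.4.8 ties its total and domain means to no instrument, and they may be meant for the other questionnaires. Even the placement of PRO-CTCAE under 10.4.8 is an inference from 2.4 and footnote 7. This stands too, but the alternative reading is that the form has no planned analysis at all.

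**The optional analysis could supply the count.** It could, but without an instrument, threshold or denominator it commits the trial to nothing.

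**The summary is more than a mean.** The maximum shows that at least one patient was severely affected, and at 3 or 6 patients the count at one visit is recoverable. It still does not show whether the symptom is new.

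**A careless count would mislead.** Follow-up runs for 3 years, through adjuvant temozolomide and progression, while AE recording stops 30 days after the last study drug (6.1). A count over every post-baseline visit would mix these periods, so a time window is needed.

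**Timing limits the data.** No form is scheduled between baseline and the end of radiotherapy, and recall is 7 days. At Levels 1 and 2 the last selinexor dose falls in week 5 of a six-week course, so the end-of-radiotherapy form may miss symptoms felt on drug. A table cannot repair this and should state it.

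**Conclusion.** The point holds as a gap in the analysis of patient-reported tolerability. PRO-CTCAE has no named analysis, and the only text that can cover it firmly plans statistics that do not give the number of patients at a dose level who newly reported a severe symptom. With nine patients, identical summaries can hide 2 versus 4 severe patients. In smaller levels the loss is mainly of whether the symptom is new.

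This rests on the assumed 0-4 coding and on the inference that 10.4.8 applies. The form covers the main symptomatic harms except diarrhea, which has no fixed item. It covers four of the seven most common events in 1.2.9, and two of the other three (thrombocytopenia and anemia) are laboratory findings.

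The MTD is set by DLTs, which use CTCAE, RTOG grading and missed doses (3.1.4), so no escalation decision is affected. The change is minor, but it replaces an ill-fitting summary with one that serves the tolerability part of the primary objective.

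**What to change.** 1. In 10.4.8, state that the total and domain means do not apply to PRO-CTCAE, and keep the mean-based summary for MDASI-BT, PROMIS and Neuro-QoL.
2. In 10.4.4, add a descriptive table by item and dose level, separately for the end of radiotherapy and the 1-month visit. It gives n/N patients whose response is in the top two categories and worse than their own baseline. For rash, count a change from No to Yes. Exclude not-applicable answers. N is the number who completed the form both at baseline and at that visit.
3. Show beside each symptom the maximum clinician CTCAE grade over the AE recording period, labelled as covering a different period from the 7-day recall.
4. Report later follow-up visits separately, as they also reflect adjuvant temozolomide and progression and fall outside the 30-day AE window.
5. State the timing limit for Levels 1 and 2 in a footnote.
6. Align the appendix letter: 2.4 and 3.5 cite the form as Appendix F, while 3.4 and 16.7 have it as Appendix G.

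The cost is a few sentences and one set of tables from data already collected. There are no added visits or forms, and no dose, DLT or clinical rule changes.

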11 COLLABORATIVE AGREEMENTS

11.1 CLINICAL TRIAL AGREEMENT (CTA)

A Clinical Trial Agreement between Karyopharm Therapeutics Inc. and the National Cancer Institute for the clinical development of Selinexor (KPT-330) has been executed (CTA # 01119-18).

12 HUMAN SUBJECTS PROTECTIONS

12.1 RATIONALE FOR SUBJECT SELECTION

Subjects of both sex and from all racial and ethnic groups are eligible if they meet eligibility criteria. To date, there is no information that suggests that differences in radiation or disease response would be expected in one group compared with another. Efforts will be made to extend accrual to a representative population, but in this preliminary study, a balance must be struck between patient safety considerations and limitations on the number of individuals exposed to potentially toxic and/or ineffective treatments on one hand and the need to explore ethnic aspects of clinical research on the other hand. If differences in outcome that correlate with ethnic identity

are noted, accrual may be expanded or a follow-up study may be written to investigate those differences more fully.

12.2 PARTICIPATION OF CHILDREN

The biology of gliomas in children is very different than the biology of adult gliomas. As such most children are treated in children oncology protocols (COG) protocols through Children's Hospital. This protocol should not compete with the excellent work being done at Children's Hospital and is thus aimed at treating adult patients.

12.3 PARTICIPATION OF SUBJECTS UNABLE TO GIVE CONSENT

Adults unable to give consent are eligible to enroll in and remain on the protocol should capacity be lost during the study as the incidence of cognitive incapacitation in the glioma population is high. Excluding them would significantly impact enrollment and our ability to meet study objectives. All subjects able to provide consent at the time of enrollment will be offered the opportunity to fill in their wishes for research and care, and assign a substitute decision maker on the "NIH Advance Directive for Health Care and Medical Research Participation" form so that another person can make decisions about their medical care in the event that they become incapacitated or cognitively impaired during the course of the study. Note: The PI or AI will contact the NIH Ability to Consent Assessment Team (ACAT) for evaluation as needed for the following: an independent assessment of whether an individual has the capacity to provide consent; assistance in identifying and assessing an appropriate surrogate when indicated; and/or an assessment of the capacity to appoint a surrogate.

Please see section [**12.5.1**](#) for consent procedure.

12.4 RISK/BENEFIT ASSESSMENT

12.4.1 Known Potential Risks

12.4.1.1 Risks from Selinexor

The primary risk from this study is increased toxicity from selinexor ([**14.1.2**](#)).

12.4.1.2 Risks of Temozolomide

Refer to package insert.

12.4.1.3 Risks from Radiation

During participation in this research study, patients will be exposed to 60 Gy from radiation therapy and a much smaller amount of radiation from a CT scan used for treatment planning.

12.4.1.4 Risks from CT Imaging Contrast Agent

Itching, hives or headaches are possible risks associated with contrast agents that may be used during CT imaging. Symptoms of a more serious allergic reaction include shortness of breath and swelling of the throat or other parts of the body. Very rarely, the contrast agents used in CT can cause kidney problems for certain patients, such as those with impaired kidney function.

12.4.1.5 Risk from MRI scans

Participants are at risk for injury from the MRI magnet if they have metal in their body. There is a possibility that participants may experience claustrophobia. There are risks of back discomfort related to lying in the scanner.

12.4.1.6 Risks from MRI Gadolinium Based Contrast Agent (GBCAs)

The most common side effects from MRI contrast (gadolinium) include injection site pain, nausea, itching, rash, headaches and dizziness. Serious but rare side effects such as gadolinium toxicity and nephrogenic systemic fibrosis, or NSF, are most often seen in patients with severe kidney problems.

12.4.1.7 Risks of Blood draws

Side effects of blood draws include pain and bruising in the area where the needle was placed, lightheadedness, and rarely, fainting. When large amounts of blood are collected, low red blood cell count (anemia) can develop. Up to 31 mL will be drawn during screening and/or baseline and up to 10 mL during follow-up.

12.4.1.8 Risks of Questionnaires

Questionnaires may contain questions that are sensitive in nature. The patients are asked to only answer questions they are comfortable with.

12.4.2 Known Potential Benefits

The potential benefits from this therapy are disease stabilization and delay or reduction of symptoms caused by the cancer, predominantly neurological impairment.

12.4.3 Assessment of Potential Risks and Benefits

A number of clinically appropriate strategies to minimize risks to patients have been built into the protocol through the means of inclusion/exclusion criteria, monitoring strategies, and management guidelines. The protocol provides for detailed and careful monitoring of all patients to assess toxicity. The potential benefit to a patient that participates in this study is better control of their tumor growth which may or may not have a favorable impact on symptoms and/or survival.

Overall, the potential benefit of the study drug combination and radiation in subjects with newly diagnosed glioblastoma and gliosarcoma outweigh the risks. This assessment applies for subjects able and unable to provide consent.

12.5 CONSENT PROCESS AND DOCUMENTATION

The informed consent document will be provided as a physical or electronic document to the participant or consent designee as applicable for review prior to consenting. A designated study investigator will carefully explain the procedures and tests involved in this study, and the associated risks, discomforts and benefits. In order to minimize potential coercion, as much time as is needed to review the document will be given, including an opportunity to discuss it with friends, family members and/or other advisors, and to ask questions of any designated study investigator. A signed informed consent document will be obtained prior to entry onto the study.

The initial consent process as well as re-consent, when required, may take place in person or remotely (e.g., via telephone or other NIH approved remote platforms used in compliance with

policy, including HRPP Policy 303) per discretion of the designated study investigator and with the agreement of the participant/consent designee(s). Whether in person or remote, the privacy of the subject will be maintained. Consenting investigators (and participant/consent designee, when in person) will be located in a private area (e.g., clinic consult room). When consent is conducted remotely, the participant/consent designee will be informed of the private nature of the discussion and will be encouraged to relocate to a more private setting if needed.

Consent will be documented with required signatures on the physical document (which includes the printout of an electronic document sent to participant) or as described below, with a manual (non-electronic) signature on the electronic document. When required, witness signature will be obtained similarly as described for the investigator and participant.

Manual (non-electronic) signature on electronic document:

When a manual signature on an electronic document is used for the documentation of consent at the NIH Clinical Center, this study will use the following to obtain the required signatures:

- Adobe platform (which is not 21 CFR Part 11 compliant); or,
- iMedConsent platform (which is 21 CFR Part 11 compliant)

During the consent process, participants and investigators will view individual copies of the approved consent document on screens at their respective locations (if remote consent); the same screen may be used when in the same location, but is not required.

Both the investigator and the participant will sign the document using a finger, stylus or mouse.

Note: Refer to the CCR SOP PM-2, Obtaining and Documenting the Informed Consent Process for additional information (e.g., verification of participant identity when obtaining consent remotely) found at: [https://nih.sharepoint.com/sites/NCI-CCR-OCD-Communications/SitePages/OEC-Administrative---Clinical-Research-\(ADCR\).aspx?Mode=Edit](https://nih.sharepoint.com/sites/NCI-CCR-OCD-Communications/SitePages/OEC-Administrative---Clinical-Research-(ADCR).aspx?Mode=Edit).

12.5.1 Consent Process for Adults Who Lack Capacity to Consent to Research Participation

For participants addressed in section **12.3**, an LAR will be identified consistent with Policy 403 and informed consent obtained from the LAR, as described in Section 12.5.

13 REGULATORY AND OPERATIONAL CONSIDERATIONS

13.1 STUDY DISCONTINUATION AND CLOSURE

This study may be temporarily suspended or prematurely terminated if there is sufficient reasonable cause. Written notification, documenting the reason for study suspension or termination, will be provided by the suspending or terminating party to investigator, the Investigational New Drug (IND) sponsor and regulatory authorities. If the study is prematurely terminated or suspended, the Principal Investigator (PI) will promptly inform study participants, the Institutional Review Board (IRB), and sponsor and will provide the reason(s) for the termination or suspension. Study participants will be contacted, as applicable, and be informed of changes to study visit schedule.

Circumstances that may warrant termination or suspension include, but are not limited to:

- Determination of unexpected, significant, or unacceptable risk to participants
- Demonstration of efficacy that would warrant stopping

- Insufficient compliance to protocol requirements
- Data that are not sufficiently complete and/or evaluable
- Determination that the primary endpoint has been met
- Determination of futility

Study may resume once concerns about safety, protocol compliance, and data quality are addressed, and satisfy the sponsor, IRB and/or Food and Drug Administration (FDA).

13.2 QUALITY ASSURANCE AND QUALITY CONTROL

The clinical site will perform internal quality management of study conduct, data and biological specimen collection, documentation and completion. An individualized quality management plan will be developed to describe a site's quality management.

Quality control (QC) procedures will be implemented beginning with the data entry system and data QC checks that will be run on the database will be generated. Any missing data or data anomalies will be communicated to the site(s) for clarification/resolution.

Following written Standard Operating Procedures (SOPs), the monitors will verify that the clinical trial is conducted and data are generated and biological specimens are collected, documented (recorded), and reported in compliance with the protocol, International Council for Harmonisation Good Clinical Practice (ICH GCP), and applicable regulatory requirements (e.g., Good Laboratory Practices (GLP), Good Manufacturing Practices (GMP)).

The investigational site will provide direct access to all trial related sites, source data/documents, and reports for the purpose of monitoring and auditing by the sponsor, and inspection by local and regulatory authorities.

